## 6.5 Analysis of safety outcomes

SAEs and ADRs that occurred during run-in will be summarised as number (percent). Post-randomisation SAE and ADR categories will be cross-tabulated with treatment group and summarised as number (percent).

## 6.6 Exploratory analyses

### 6.6.1 Sub-study participation

The number (percentage) of participants who consented to participate in and who completed the home blood pressure sub-study. Number (percentage) of participants who consented to participate in and who completed the twenty-four hour ambulatory blood pressure sub-study.

### 6.6.2 Intradialytic hypotension

The incidence rate of intradialytic hypotension during run-in will be estimated using an intercept-only Poisson regression model. A Poisson regression model with treatment group as a covariate will be used to compare incidence rates for intradialytic hypotension in the randomised carvedilol and placebo groups.

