### **1.2 Study synopsis**

The BLOCADE trial is a feasibility study for a large multi-centre, randomised, placebo-controlled trial of the effectiveness of the beta-blocker carvedilol to reduce cardiovascular morbidity and mortality in high-risk patients receiving dialysis. The multi-centre feasibility study had a six week active run-in period during which all participants received carvedilol. After the run-in period participants who tolerated carvedilol were randomised 1:1 to receive carvedilol (experimental intervention) or placebo (control intervention).

The BLOCADE feasibility study began recruiting patients on 16 May 2011 and stopped recruiting on 28 February 2013 due to slow recruitment and lack of funds to continue recruiting participants. In total, 88 participants from 11 sites were consented into the study. Of these, 72 participants from 9 sites entered the run-in phase and 49 participants from 8 sites were randomised. The final end-of-study visit was conducted in June 2014. The central database is expected to be available for analysis by the end of June 2014.

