## 2.3 Tertiary (exploratory) objectives

Exploratory objectives include assessment of intradialytic hypotension during run-in and in response to random allocation to treatment.

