## 3. STUDY DESIGN ISSUES

### 3.1 Overview

The BLOCADE trial is a phase III, randomised, double-blind, placebo-controlled, parallel group feasibility study with a six week open-label active run-in phase during which all participants received carvedilol up to a maximum dose of 6.25 mg twice daily. Participants who tolerated this dose for at least two weeks prior to the randomisation visit were randomised to carvedilol or placebo. After randomisation, participants were up-titrated to a maximum dose of 25 mg twice daily of carvedilol or placebo over a period of six weeks (plus another 4 weeks if needed), then followed for 12 months before being down-titrated off study drug over a period of four weeks.

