### **3.4 Treatment allocation**

Participants who tolerated a twice daily 6.25 mg dose of carvedilol by the end of the run-in phase were randomised 1:1 to one of the two treatment groups. Randomisation was conducted using an interactive voice response system (IVRS). The IVRS randomised patients by an adaptive allocation algorithm designed to minimise study site and dialysis modality (haemodialysis or peritoneal dialysis) imbalance within the two treatment groups.

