## 6.4 Analysis of secondary outcomes

All randomised participants with outcome data will be analysed according to the Intention-to-Treat (ITT) principle. The full analysis set will exclude randomised participants who withdrew from the study before any follow-up data on BNP or EQ5D was collected. BNP and EQ5D will be separately analysed using a linear mixed model with treatment group and baseline measurements as fixed effects and participant identifier and study visit as random effects. If there is insufficient data to reliably estimate random effects, the BNP and EQ5D data will be analysed using analysis of covariance (ANCOVA). Separate analyses will be performed on data from the 6 and 12 month visits. In all analyses, the effect of intervention group on outcome will be adjusted for baseline measurements. In addition, a logistic regression model will be used to predict successful completion of run-in (no, yes) from baseline BNP measurements.

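### The between-arm comparison of intradialytic hypotension leaves out the run-in (R2) record, which costs precision; adding it also requires a variance that allows for overdispersion (minor, exploratory outcome)

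*SAP*

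**What the plan says.** Section 2.3 sets the aim: "Exploratory objectives include assessment of intradialytic hypotension during run-in and in response to random allocation to treatment". Section 6.6.2 serves it with two separate models. For the run-in: "The incidence rate of intradialytic hypotension during run-in will be estimated using an intercept-only Poisson regression model". For the randomised phase: "A Poisson regression model with treatment group as a covariate will be used to compare incidence rates for intradialytic hypotension". The run-in data do not enter the second model. No offset, random effect or variance correction is named.

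In the schedule (3.6), read by column position, IDH is recorded at R2 and then at T2, T4, F3 and F6. There is no IDH record at BA or R0. R2 falls in a "six week open-label active run-in phase during which all participants received carvedilol up to a maximum dose of 6.25 mg twice daily" (3.1).

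On numbers, 1.2 reports that "72 participants from 9 sites entered the run-in phase and 49 participants from 8 sites were randomised". Under 3.4 those participants "were randomised 1:1 to one of the two treatment groups", by an algorithm "designed to minimise study site and dialysis modality (haemodialysis or peritoneal dialysis) imbalance within the two treatment groups".

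For BNP and EQ5D, 6.4 says: "In all analyses, the effect of intervention group on outcome will be adjusted for baseline measurements".

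**The concern.** R2 measures the same outcome in the same participant before allocation. Allocation cannot affect it, so it is a legitimate covariate, and it is likely to be the best available predictor of later IDH. Minimisation balanced site and modality, not IDH tendency. With so few participants, a handful who are prone to IDH can fall mostly into one arm. The planned model would pass that imbalance into the rate ratio, although data that could remove much of it are already scheduled.

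At stake is how the one randomised comparison of IDH is read. The run-in rate cannot stand in for it, because no IDH was scheduled before carvedilol was started.

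**Working it through.** **The plan's own figure.** The SAP gives none for IDH. Its only precision figure (3.3: 70% tolerability, n = 150, limits 62.5% and 77.5%) reproduces as 0.70 ± 2 × √(0.70 × 0.30/150) = 0.70 ± 0.075. It has no bearing here.

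**Inputs from the SAP.** 49 randomised, 1:1; one IDH record before randomisation and four after; treatment group the only covariate.

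**Assumed inputs (not in the SAP).** 20 participants per arm with IDH data; 6 sessions per record, so 6 at R2 and 4 × 6 = 24 after; mean 0.1 or 0.2 episodes per session; log-normal participant effects with SD 0.7, 1.0 or 1.3 on the log scale; no treatment effect.

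**Step 1: closed-form check, log-scale SD 1.0, no R2.** Variance of the log rate ratio ≈ 2 × [(e^(SD²) − 1)/20 + 1/(expected episodes per arm)].
- Rate 0.1: episodes per arm 20 × 24 × 0.1 = 48. True SD ≈ √(2 × [1.718/20 + 1/48]) = 0.46. A plain Poisson model counts only the second term: √(2/48) = 0.20.
- Rate 0.2: 96 episodes per arm. True SD ≈ √(2 × [1.718/20 + 1/96]) = 0.44; plain Poisson √(2/96) = 0.14.

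**Step 2: simulated gain from adding log(R2 count + 0.5)** (1,500 trials per setting). Variance reduction = 1 − (SD with R2 / SD without)².

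| Rate | Log-scale SD | Empirical SD without R2 | With R2 | Variance reduction |
|---|---|---|---|---|
| 0.1 | 0.7 | 0.316 | 0.296 | 12% |
| 0.1 | 1.0 | 0.456 | 0.357 | 39% |
| 0.1 | 1.3 | 0.608 | 0.411 | 54% |
| 0.2 | 0.7 | 0.284 | 0.240 | 29% |
| 0.2 | 1.0 | 0.424 | 0.283 | 55% |
| 0.2 | 1.3 | 0.594 | 0.313 | 72% |

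The values without R2 at log-scale SD 1.0 agree with step 1. A further run at that SD gave 0.42 to 0.35 (31%) at rate 0.1 and 0.42 to 0.28 (56%) at rate 0.2, so these figures are approximate.

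**Step 3: different assumptions** (gamma participant effects with variance 1 or 2; 36 or 49 participants; 3 or 6 sessions per record). The SD reduction runs from 0.473 to 0.445 (variance −11%) up to 0.441 to 0.274 (variance −61%). With no heterogeneity there is no gain: for example, 0.186 without R2 and 0.188 with it.

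**Step 4: effect of an observed imbalance** (step 3 settings with heterogeneity, no true effect). In the quarter of trials most imbalanced on R2, the mean rate ratio towards the arm with more run-in IDH was 1.26 to 1.79 without R2 and 0.98 to 1.03 with it.

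**Step 5: does R2 alone give a valid test?** In the step 2 setting at log-scale SD 1.0, the SE reported by the plain Poisson model does not fall: 0.21 to 0.22 (rate 0.1) and 0.15 to 0.15 (rate 0.2). With R2 at rate 0.1, the test rejects when |Z| > 1.96 × 0.22/0.357 = 1.21, or about 23% of the time. At rate 0.2 the threshold is 1.96 × 0.15/0.283 = 1.04, or about 30%. Simulation gave 24% and 30%. False positives at nominal 5% over the step 3 settings with heterogeneity:

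| Model | All trials | Most imbalanced quarter |
|---|---|---|
| Planned | 17%–55% | – |
| R2, plain Poisson SE | 13%–31% | – |
| Scaled SE, no R2 | 5%–7% | 7%–18% |
| R2 and scaled SE | 4%–8% | 4%–10% |

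**The case against.** The strongest reply is that randomisation already deals with chance imbalance. The unadjusted estimate is right on average, and a correct standard error covers the rest. This stands as far as it goes. A reader might infer that 6.6.2 yields a biased carvedilol effect. It does not: simulated under no effect, the mean log rate ratio stayed within 0.02 of zero with or without R2. Most of the excess false positives come from the plain Poisson variance, not from omitting R2. A corrected variance alone, however, leaves the lost precision and the 7% to 18% error rate when the arms are visibly imbalanced.

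Other stronger readings also fail:
- That 6.6.2 contradicts 6.4. The sentence in 6.4 sits among the BNP and EQ5D analyses and does not reach IDH. The contrast shows a difference in treatment without a stated reason, not a contradiction.
- That every participant has an R2 record. The schedule row carries no modality restriction, but the trial enrols peritoneal dialysis patients, IDH is defined and tabulated around dialysis sessions, and the SAP does not say how these patients are handled. Nor does it give the number on haemodialysis, so 20 per arm is an assumption.
- That R2 is an untreated baseline, or one on a uniform dose. It was recorded on open-label carvedilol at doses up to a stated maximum, and planned Table 7 splits participants by final run-in dose. It remains a valid pre-randomisation covariate.

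Finally, this is a tertiary outcome in a feasibility study, and the SAP's preface allows supporting exploratory analyses. That limits the severity.

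**Conclusion.** The point holds as a minor one. The planned IDH comparison omits a pre-randomisation measurement of the same outcome that the trial schedules. If participants differ in IDH tendency, the cost is lost precision and exposure to chance imbalance, not systematic bias. Across the assumed settings with heterogeneity, the recoverable share of the variance is roughly 10% to 70%; without heterogeneity it is nil. Event rate, sessions per record, heterogeneity and the number of participants contributing IDH data are all assumptions. The documents do not support the inference that adding R2 would by itself make the test valid. The variance must be corrected as well.

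**What to change.** In 6.6.2, specify for the post-randomisation model:
- the participant's R2 IDH rate as a covariate, for example log((episodes + 0.5)/recorded sessions);
- log(number of recorded sessions) as an offset;
- a variance that allows for repeated sessions and for differences between participants: a scaled or robust SE, a negative binomial model, or a participant random effect.

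State that R2 was measured on open-label run-in carvedilol and is not an untreated baseline.

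The cost is a few lines of SAP text and no new data. The downside is that participants without an R2 record need a missing-value rule, such as a missing indicator, and that rule should say how peritoneal dialysis participants enter the analysis. The change belongs before unblinding. Made later, it should be reported as unplanned, as 5.2 requires.

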### **4.3 Tertiary outcomes**

Outcomes for exploratory analyses are:

- 1) The proportion of participants who consented to participate in and completed the home blood pressure and twenty-four hour ambulatory blood pressure sub-studies.
- 2) Intra-dialytic hypotension (no, yes), defined as a fall in systolic blood pressure of at least 20 mm Hg during or post dialysis relative to pre-dialysis associated with symptoms of hypotension (nausea/vomiting, cramps/pain in legs, dizzy/light headed, syncope/pre-syncope/loss of consciousness, chest or abdominal pain, other symptom) and requiring treatment for hypotension (head-low position, modification of ultrafiltration rate or target, infusion of any type of intravenous fluid specifically to treat hypotension, other treatment for hypotension).

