## 6.3 Analysis of primary outcomes

### 6.3.1 Tolerability

Binomial proportions and 95% confidence intervals for the proportion of participants who completed run-in will be estimated using an intercept-only Generalised Linear Model from the binomial family with identity link function. Binomial proportions and 95% confidence intervals for randomised participants who drop out from carvedilol and placebo will be estimated using the same statistical model. Incidence rates for major adverse events (symptomatic hypotension and symptomatic bradycardia) in the randomised carvedilol and placebo groups will be estimated using intercept-only Poisson regression models.

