### 8.1 Planned tables

The following are planned summary tables:

- Table 1. Reasons screened patients were not consented into the study
- Table 2. Enrolment by study centre
- Table 3. Stratification variables by treatment group for randomised participants
- Table 4. Withdrawals, protocol deviations and violations during run-in
- Table 5. Withdrawals, protocol deviations and violations by treatment group
- Table 6. Demographic and clinical baseline characteristics for participants who entered run-in, overall and by successful completion of run-in (yes, no) [Table note indicating 16 consented participants did not enter run-in]
- Table 7. Demographic and clinical baseline characteristics by final run-in dose for all participants who entered run-in
- Table 8. Demographic and clinical baseline characteristics by treatment group for randomised participants
- Table 9. Number (percent) for primary outcomes of feasibility, sample size and logistics
- Table 10. Number of proposed primary and secondary outcomes for large clinical endpoint study
- Table 11. Intradialytic hypotensive episodes per dialysis session during run-in
- Table 12. Intradialytic hypotensive episodes per dialysis session overall and by treatment group for randomised participants
- Table 13. Number (percentage) of dialysis sessions during which an intradialytic hypotensive event occurred during run-in
- Table 14. Number (percentage) of dialysis sessions during which an intradialytic hypotensive episode occurred overall and by treatment group for randomised participants
- Table 15. SAEs and ADRs during run-in, overall and by successful completion of run-in (yes, no)
- Table 16. SAEs and ADRs by treatment group for randomised participants

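### The plain Poisson analysis of intradialytic hypotension (SAP 6.6.2) makes no allowance for repeated sessions in the same participant, so its intervals are too narrow if participants differ in proneness and contribute more than a few sessions

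*SAP*

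**What the plan says.** SAP 6.6.2 gives IDH two models. For run-in: "The incidence rate of intradialytic hypotension during run-in will be estimated using an intercept-only Poisson regression model". After randomisation: "A Poisson regression model with treatment group as a covariate will be used to compare incidence rates for intradialytic hypotension". Neither sentence names an offset, a participant effect, a robust variance or an allowance for overdispersion.

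The data are defined by session. Section 4.3 has "Intra-dialytic hypotension (no, yes), defined as a fall in systolic blood pressure of at least 20 mm Hg during or post dialysis", which ties the event to a dialysis session. In section 8.1, Table 12 is "Intradialytic hypotensive episodes per dialysis session overall and by treatment group for randomised participants" and Table 14 is "Number (percentage) of dialysis sessions during which an intradialytic hypotensive episode occurred overall and by treatment group for randomised participants". Tables 11 and 13 do the same for run-in. The schedule in section 3.6 appears to place IDH recording at R2 before randomisation and at T2, T4, F3 and F6 after it.

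Other repeated outcomes are handled differently. Section 6.3.3 (dose by visit) and section 6.4 (BNP and EQ5D) both put a participant random effect in the model.

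On numbers, section 1.2 says: "Of these, 72 participants from 9 sites entered the run-in phase and 49 participants from 8 sites were randomised". Section 3.4 says that participants "were randomised 1:1 to one of the two treatment groups". Section 2.3 and the heading of 6.6 make IDH an exploratory outcome.

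**The concern.** A Poisson model sets the variance of the event count equal to its mean. That fails when some participants are more prone to IDH than others, because sessions from one person then resemble each other. The model counts each session as separate information about the treatment effect, while the true unit of replication is the participant.

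Collapsing the data to one count per participant with an offset does not help. The Poisson likelihood for the arm effect depends only on total events and total sessions per arm, so the estimate and its standard error, √(1/E₁ + 1/E₀) with E the events in each arm, stay the same and the excess variance stays unmodelled.

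At stake are the width of the run-in interval and the reliability of the between-arm rate ratio. The primary tolerability outcomes in 6.3.1 are estimated within each arm and the safety outcomes in 6.5 are tabulated, so this is the SAP's only between-arm model of a hypotension outcome. With 49 randomised, a few prone participants falling in one arm could look like a drug effect.

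**Working it through.** The SAP states no power, alpha or expected rate for IDH, so there is no figure of its own to reproduce. The check asks how far the nominal error rate moves over plausible inputs.

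**Inputs from the SAP:** 49 randomised, 1:1; plain Poisson with treatment as the only term; session-level counting.

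**Assumed, because the SAP does not give them:** two-sided 5% test; 20 haemodialysis participants per arm; m = 4 to 24 recorded sessions each; 3 to 10 episodes per 100 sessions; coefficient of variation (CV) of the participant rate 0.5 to 1.5.

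**Check 1: gamma-Poisson counts**

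With mean count μ = m × rate, the dispersion is D = 1 + CV² × μ. The true standard error is √D times the Poisson one. The approximate error rate is 2 × (1 − Φ(1.96/√D)).

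- 24 sessions, 5 per 100, so μ = 1.2. CV 1.0: D = 1 + 1 × 1.2 = 2.2, √D = 1.48, approximate error rate 19%. CV 1.5: D = 1 + 2.25 × 1.2 = 3.7, √D = 1.92, approximate error rate 31%.
- 24 sessions, 10 per 100, CV 1.5, so μ = 2.4: D = 1 + 2.25 × 2.4 = 6.4, √D = 2.53, approximate error rate 44%.
- 4 sessions, 5 per 100, CV 1.5, so μ = 0.2: D = 1 + 2.25 × 0.2 = 1.45, √D = 1.20, approximate error rate 10%. Only 20 × 0.2 = 4 events per arm are expected, so the large-sample formula overstates the error rate and simulation is needed.

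Simulated error rate of the plain Poisson Wald test with no treatment effect:

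| Sessions | Episodes per 100 | CV | Error rate |
|---|---|---|---|
| 4 | 3 to 5 | 1.0 to 1.5 | 0.3% to 3.2% |
| 4 | 10 | 1.0 to 1.5 | 7% to 12% |
| 12 | 3 to 10 | 0.5 | 4% to 8% |
| 12 | 3 | 1.0 | 6% |
| 24 | 5 | 1.0 | 18% |
| 24 | 5 | 1.5 | 29% |
| 24 | 10 | 1.5 | 43% |

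A participant-clustered variance brings the 24-session settings back to about 6% to 8%.

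**Check 2: yes/no per session, all 49 participants**

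With p the probability of IDH in a session and ICC the within-participant correlation, the variance relative to Poisson is (1 − p)(1 + (m − 1) × ICC). At m = 12 and p = 0.10:

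| ICC | Variance ratio | SE ratio | Plain Poisson, simulated | Clustered variance, simulated |
|---|---|---|---|---|
| 0.05 | 0.9 × 1.55 = 1.40 | 1.18 | 9.3% | 5.0% |
| 0.10 | 0.9 × 2.10 = 1.89 | 1.37 | 14.8% | 5.3% |
| 0.20 | 0.9 × 3.20 = 2.88 | 1.70 | 24.5% | 5.6% |

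The Poisson standard error becomes too small once the ICC exceeds p/((1 − p)(m − 1)). That is 0.1/(0.9 × 11) = 0.010 at 12 sessions and 0.1/(0.9 × 3) = 0.037 at 4 sessions. At ICC zero and m = 12 the plain test is slightly conservative (3.7%).

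**Run-in rate.** The same variance ratio applies to the intercept-only model, so its interval is too narrow by the same square-root factor.

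**The case against.** The strongest reply is that the size of the problem cannot be read from the SAP. Section 3.5 says only that IDH was recorded over specific times, and the schedule is compatible with one session at each of four post-randomisation visits. With 4 sessions and 3 to 5 episodes per 100, the plain test does not exceed 5%. This stands. A reader might infer that the false-positive rate is certainly inflated, but the documents support only the conditional statement.

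It can also be said that the outcome is exploratory and carries no alpha, decision rule or go/no-go role. This stands too. The inference that a spurious IDH difference would steer the large trial goes beyond the text.

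Two extensions are tempting and do not hold:

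- **The event rates in 6.3.1.** Symptomatic hypotension and bradycardia "will be estimated using intercept-only Poisson regression models", separately by arm. No between-arm test is planned, so a type I error does not arise, and the SAP does not say whether first or all events are counted. Within-participant recurrence is therefore not shown to matter there.
- **The missing adjustment for the run-in (R2) IDH rate.** An unadjusted randomised comparison is valid. Adjustment could gain precision, but leaving it out is no error.

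None of this defends the plain Poisson variance. A reading in which each participant supplies a single yes/no would remove the problem, but it does not fit Tables 11 to 14.

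**Conclusion.** The point holds in conditional form. SAP 6.6.2 applies a model that assumes independent sessions to data that the SAP's own tables count by session in the same participants, and it departs from the SAP's handling of other repeated outcomes in 6.3.3 and 6.4. The direction is clear: if participants differ in proneness and contribute more than a few sessions, both the run-in interval and the between-arm interval are too narrow.

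The size rests on assumptions. With 20 haemodialysis participants per arm and the input ranges above, the nominal 5% test runs from no inflation at all to about 43%. The middle case of 24 sessions and 5 episodes per 100 gives 18% to 29%. The change is worth making because it costs almost nothing, but the matter is moderate at most, since IDH is exploratory.

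**What to change.** Change section 6.6.2 only. Suggested wording:

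> IDH rates will be estimated by Poisson regression with the log of the number of recorded dialysis sessions as offset. Standard errors will be clustered on participant, with a small-sample correction. This applies to the run-in rate and to the treatment comparison, which will be reported as a rate ratio with 95% confidence interval.

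A negative binomial model on per-participant counts, with the same offset, is an acceptable alternative if the clustered Poisson model is named as the fallback for non-convergence. Adjustment for the R2 rate can be left as an option. Section 6.3.1 needs no change on this account.

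The cost is a wording change and no new data. Intervals for an exploratory outcome will be wider where clustering is present. The clustered test is not perfect at this sample size: it can still run somewhat liberal, at about 6% to 11%, when events are rare and within-participant correlation is high.
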